4.5.1.2. Selection of 5 mg/day

In addition to 3 mg/day, this study will also evaluate a higher dose at 5 mg/day, on the basis of retrospective and exploratory exposure-response analyses, conducted by both Biogen and independent investigators, demonstrating increased efficacy of BIIB093 with higher exposures, as detailed below.

A retrospective analysis of Study 201, a pilot study of BIIB093 in LHI, dichotomized participants into low and high exposure cohorts. Analysis of efficacy data by exposure demonstrated improved mitigation of vasogenic edema (measured by T2 Flair MRI) with higher BIIB093 exposures (average concentration of 32 ng/mL) versus lower plasma levels (average concentration 16 ng/mL) [Kimberly 2014]. Notably, 25 ng/mL is the target concentration for 3 mg/day. Additionally, an exploratory analysis using data from Study 203 (pivotal Phase 2 LHI study) showed a consistent trend of higher BIIB093 exposure correlating with improved efficacy outcome (reduction of midline shift). A relationship between increasing BIIB093 exposure and decreasing matrix metalloprotease-9 (MMP-9) concentration was also observed, suggesting improved blood-brain- barrier integrity in the presence of higher BIIB093 drug exposure. Therefore, greater efficacy is anticipated for brain contusion at the higher dose of BIIB093.

The specific dose level at 5 mg/day was selected based on a totality of clinical safety (severe hypoglycemia) and pharmacodynamics (PD) data (blood glucose). Up to 10 mg/day has been previously evaluated in the first-in-human study in healthy participants (Study 101).

Symptomatic severe hypoglycemia, or BG < 55 mg/dL (~3.1 mmol/L), was observed in 6 mg/day and 10 mg/day cohorts, and 3 mg/day was the highest dose studied that did not result in severe hypoglycemia. Doses between 3 and 6 mg/day have not been evaluated clinically. No apparent exposure-response relationship between BIIB093 plasma concentration and BG level was observed. As such, safety results from Study 101 were used to inform the clinical concentration threshold for severe hypoglycemia, which was 75 ng/mL. PK simulations of the anticipated exposures at 5 mg/day (mean plasma concentration at steady state: 40 ng/mL, 95% CI: 13.4, 61.8) showed the maximum predicted BIIB093 plasma concentration would remain below the threshold where severe hypoglycemia was observed.

Furthermore, the exposures of 5 mg/day dose level are covered within the safety margin established in BIIB093 preclinical studies. A 14-day toxicity study in adult rats was conducted to assess safety and tolerability of BIIB093. During the 14-day continuous infusion period, no BIIB093-related clinical observations were noted, but clinical chemistry results showed pharmacologic hypoglycemia in female rats. A sex difference was noted in rats as exposure to BIIB093 was generally higher in female rats compared with male rats; however, combined male and female rat exposure is used to generate exposure margins because a sex difference is not observed in humans. The no observed adverse effects level was considered to be 18.2 mg/kg, which provides exposure margins of 3-fold and 6-fold based on the maximum observed concentration and concentration at steady state (C_{ss}), respectively, at 5 mg/day. The exposure data at 5 mg/day are the result of simulations. A dose range of 3 mg/day to 5 mg/day has a limited dynamic range but, based on preclinical data, appears to balance safety and the opportunity to maximize efficacy.

CONFIDENTIAL

The information contained herein may not be used, disclosed, or published without the written consent of Biogen MA Inc.

4.5.1.3. IV Infusion Duration

For the brain contusion program, the BIIB093 treatment period will be extended to 96 hours, as opposed to the 72-hour infusion period implemented in participants with LHI. An extended treatment period is believed to be of additional benefit to patients with brain contusion because intracranial pressure monitoring in the intensive care unit (ICU) is typically carried out for 4 to 5 days in these patients, and HPC and edema can occur as late as 3 to 4 days after head injury [Kurland 2012; Staykov 2011]. Dosing out to 96 hours will ensure that BIIB093 continues to affect the evolution of the hematoma and its surrounding edema, which tends to occur later in patients with brain contusion than in patients with a malignant infarction.

During the additional 24-hour infusion period, the same plasma C_{ss} will be maintained for BIIB093. While the overall drug exposure is increased, it is still within the safety margin established for BIIB093. It is also important to note that with the daily dose of 5 mg, the systemic exposure of BIIB093 acute treatment is significantly lower than that of the approved therapeutic oral glibenclamide (maximum dose of 20 mg/day approved for Micronase® or 12 mg/day approved for Glynase®) taken chronically by patients with diabetes.

Risk mitigation strategies will be applied for the occurrence of hypoglycemia (administration of IV dextrose or discontinuation/dose reduction/interruption of BIIB093, at the discretion of the Investigator) [see Section 11.4.1.1.1]. Based on the evidence available, the plasma C_{ss} is not expected to change; therefore, AEs are expected to be consistent with clinical studies to date, with hypoglycemia being the principal risk. Specific risk mitigation strategies are advised and for unmanageable hypoglycemia, discontinuation criteria are in place (see Section 10.1).

CONFIDENTIAL

The information contained herein may not be used, disclosed, or published without the written consent of Biogen MA Inc.

5. SCHEDE OF ACTIVITIES

CONFIDENTIAL

The information contained herein may not be used, disclosed, or published without the written consent of
Biogen MA Inc.

Table 2: Schedule of Activities

	Screening/ Enrollment	Hours 0-12 ¹	Hour 24 (±6 h)	Hour 48 (±12 h)	Hour 72 (±12 h)	Hour 96 (±12 h) ²	Day 7 (±24 h) ³	Hospital Discharge (±24 h) ⁴	Day 30 (±7 d) ⁴	Day 90 (±14 d) ⁴	Day 180 (±14 d) ⁴	NSx/Comfort Measures (if applicable)	ET Visit
Inclusion/ exclusion criteria	X												
Informed consent	X												
Demographics, medical history, physical examination (including weight and height)	X												
TT/LKN	X												
NCCT ⁵	X ⁶		X			X ⁷						X	
GCS	X		X	X		X							
Pregnancy test (urine or serum)	X												
Blood alcohol level	X												
Blood sampling for coagulation panel (INR, PTT, fibrinogen)	X												
Blood sampling for hematology and blood chemistry	X							X					X ⁸
Blood sampling for LFTs	X		X	X	X	X	X						
Vital signs ⁹	X	X	X	X	X	X	X						X
Other assessments (ECG, [REDACTED])	(see Table 3 for ECG, [REDACTED] schedule of activities)												
Blood sampling for pharmacogenetics (optional) ¹⁰						X							
Enrollment/randomization (TT/LKN < 10 h)	X												

CONFIDENTIAL

The information contained herein may not be used, disclosed, or published without the written consent of Biogen MA Inc.

	Screening/ Enrollment	Hours 0-12 ¹	Hour 24 (±6 h)	Hour 48 (±12 h)	Hour 72 (±12 h)	Hour 96 (±12 h) ²	Day 7 (±24 h) ³	Hospital Discharge (±24 h) ⁴	Day 30 (±7 d) ⁴	Day 90 (±14 d) ⁴	Day 180 (±14 d) ⁴	NSx/Comfort Measures (if applicable)	ET Visit
Study treatment (TT/LKN < 10 h)			← 96-hour infusion → (see Section 4.5.1 for further details)										
Delayed intubation eCRF ¹¹			X	X	X	X							
BG measurement ¹²	X	X	X	X	X	X	X						
Concomitant therapy	X	X	X	X	X	X	X	X	X	X	X	X	X
Concomitant procedures ¹³	X	X	X	X	X	X	X	X	X	X	X	X	X
Craniectomy/comfort care/ cranioplasty assessment form(s)												X	
MRI ^{14, 5}						X ¹⁵						X	X ¹⁶
GOS-E								X	X	X	X		X
mRS										X	X		X
Review safety data and record AEs/SAEs ¹⁷	X	X	X	X	X	X	X	X	X	X	X		X
Brief suicide ideation/behavior assessment ¹⁸	X								X	X	X		X

AE = adverse event; BG = blood glucose; CMO = comfort measures only; d = days; DC = decompressive craniectomy; ECG = electrocardiogram; eCRF = electronic case report form; ET = early termination; [REDACTED]; GCS = Glasgow Coma Scale; GOS-E = Glasgow Coma Scale-Extended; h = hours; INR = international normalized ratio; IPH = intraparenchymal hematoma; LFT = liver function test; LKN = last known normal; MRI = magnetic resonance imaging; mRS = modified Rankin Scale; NCCT = noncontrast computed tomography; NSx = neurosurgical intervention; [REDACTED] PTT = partial thromboplastin time; [REDACTED]; SAE = serious adverse event; SOC = standard of care; TT = time of trauma.

CONFIDENTIAL

The information contained herein may not be used, disclosed, or published without the written consent of Biogen MA Inc.

¹ Hour 0 is defined as the start of study treatment infusion.

² In the event a participant is discharged from the hospital prior to Hour 96, every effort should be made to obtain neuroimaging (NCCT or MRI) prior to discharge.

³ If a participant is due to be discharged from hospital prior to Day 7, every effort should be made to perform the Day 7 assessments at the time of discharge or just prior.

⁴ All visits after hospital discharge can be conducted by telephone; however, the Day 90 and Day 180 Visits should be in person whenever possible. Should the follow-up visits at Day 90 and Day 180 be conducted remotely, [REDACTED].

⁵ Scans (NCCT or MRI) obtained within 12 hours of IPH evacuation, DC, or CMO meet the requirement. Scans are not expected for other NSx interventions. If IPH evacuation, DC, or CMO are indicated prior to 96 hours, an NCCT or MRI scan in the 12 hours proceeding the procedure should be collected, and no further post procedural images are required beyond SOC.

⁶ NCCT as SOC at Screening (prior to enrollment). If not eligible per SOC scan, a single, repeat, study-specific NCCT may be obtained to reassess contusion volume if feasible within the protocol-specified time window.

⁷ Optional Hour 96 NCCT should be obtained in addition to the MRI whenever possible, after study treatment infusion is complete, within 18 hours of the Hour 96 timepoint.

⁸ Only performed if participant has not yet been discharged from hospital.

⁹ Vital signs include temperature, pulse rate, systolic and diastolic blood pressure, respiratory rate, and oxygen saturation. Measurements taken nearest to the assessment timepoint should be recorded.

¹⁰ The optional blood sample for pharmacogenetic analysis requires a separate informed consent form to be administered between the start of study and hospital discharge. The pharmacogenetic sample should be collected as close to the consenting procedure as possible and preferably within 24 hours of the start of study treatment. The date and time of collection should be recorded.

¹¹ A delayed intubation eCRF must be completed if a participant is intubated for deteriorating neurologic status.

¹² Hourly (\pm 30 minutes) for Hour 0 to Hour 24, every 2 hours (\pm 30 minutes) for Hour 25 to Hour 48, and every 4 hours (\pm 60 minutes) for Hour 49 to Hour 96. If treatment for low BG (< 70 mg/dL [\sim 3.9 mmol/L]) is initiated, then BG monitoring is required every 15 minutes (\pm 10 minutes) until BG is \geq 80 mg/dL (\sim 4.4 mmol/L) for 3 consecutive readings without exogenous bolus glucose supplementation. See Section 11.4.1.1.1 for details on BG monitoring and management.

¹³ [REDACTED] A CMO eCRF must be completed for participants for whom care is withdrawn.

¹⁴ An NCCT scan is sufficient for participants who cannot get an MRI.

¹⁵ The 96 hour scan should be performed after study treatment infusion is complete, within 18 hours of the Hour 96 time point.

¹⁶ Only required if ET occurs before the Hour 96 scan has been performed.

¹⁷ Includes all AEs from the beginning of study treatment administration and all SAEs from the time of consent. AEs of special interest (hypoglycemia [BG < 55 mg/dL (\sim 3.1 mmol/L)]) will be upgraded to an SAE. See Section 15.3 for further details on monitoring and recording AEs.

¹⁸ A short suicidal ideation/behavior questionnaire will be conducted on participants who are alert and capable of providing answers at Screening (prior to dosing). For these participants, this questionnaire should be repeated at Days 30, 90, 180, and ET Visit. The questionnaire conducted at Screening will record “Life Time” events and subsequent visits (at Days 30, 90, 180, and ET Visit) will record “Since the Last Visit” events.

CONFIDENTIAL

The information contained herein may not be used, disclosed, or published without the written consent of Biogen MA Inc.

Table 3: ECG, [REDACTED] Schedule of Activities

	12-lead ECG¹	
Predose	SOC ECG taken at Screening	
Minute 5	±5 minutes	
Hour 6	±5 minutes	
Hour 24	±5 minutes	
Hour 48	±5 minutes	
Hour 72	±5 minutes	
Hour 96	±5 minutes	

BG = blood glucose; ECG = electrocardiogram; [REDACTED]; SAE = serious adverse events;

SOC = standard of care.

¹ After the start of study treatment infusion, ECG must be collected before blood sampling for [REDACTED]

CONFIDENTIAL

The information contained herein may not be used, disclosed, or published without the written consent of
Biogen MA Inc.

6. STUDY OBJECTIVES AND ENDPOINTS

Primary Objective	Primary Endpoint
To determine if BIIB093 reduces brain contusion expansion by Hour 96 when compared to placebo. Measurements of contusion expansion are based on a comparison of the baseline images and the scans collected prior to and including 96-hour scan, or the scan obtained prior to DC, intraparenchymal hematoma (IPH) evacuation, or comfort measures only (CMO), if earlier.	Change in total contusion volume (hematoma plus perihematomal edema) as measured by brain imaging from baseline to 96 hours or prior to DC, IPH evacuation, or CMO if these procedures occur before 96 hours per the central review.
Secondary Objectives	Secondary Endpoints
To evaluate the effects of BIIB093 on acute neurologic status, functional outcomes, and treatment requirements.	
 • Glasgow Outcome Scale – Extended (GOS-E) at Day 180 • Modified Rankin Scale at Day 90 • Proportion of participants requiring delayed intubation 
Note: delayed intubation is defined as participants requiring intubation (for neurologic deterioration only) at any time between 24 hours and 96 hours postinjury.

To further differentiate the mechanism of action of BIIB093 compared to placebo on contusion expansion by examining differential effects on hematoma and edema expansion.	
 • Change in total contusion volume (hematoma plus perihematomal edema) as measured by brain imaging from baseline to 24 hours or prior to DC, IPH evacuation, or CMO if these procedures occur before 24 hours per the central review. • Change in absolute hematoma volume from baseline to 24 hours • Change in absolute edema volume from baseline to 96 hours

CONFIDENTIAL

The information contained herein may not be used, disclosed, or published without the written consent of
Biogen MA Inc.

To determine if BIIB093 improves survival at Day 90 when compared to placebo.	Time to all-cause death, including neurological death, through Day 90.
[REDACTED]	[REDACTED]
[REDACTED]	[REDACTED] [REDACTED]
[REDACTED]	[REDACTED]
[REDACTED]	[REDACTED] [REDACTED] [REDACTED] [REDACTED] [REDACTED] [REDACTED] [REDACTED]
[REDACTED]	[REDACTED]
[REDACTED]	[REDACTED]

CONFIDENTIAL

The information contained herein may not be used, disclosed, or published without the written consent of
Biogen MA Inc.

[REDACTED]	[REDACTED]

CONFIDENTIAL

The information contained herein may not be used, disclosed, or published without the written consent of
Biogen MA Inc.

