### **Change in Absolute Hematoma Volume from Baseline to 24 Hours**

Change in absolute hematoma volume from baseline to 24 hours will be analyzed in the Day 4 database for the full analysis set.

- ANCOVA will be performed to compare the mean change between BIIB093 combined and placebo groups based on the observed data.
- By-visit mean and change in absolute hematoma volume from baseline will be summarized.

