### Change in Absolute Edema Volume from Baseline to 96 Hours

Change in absolute edema volume from baseline to 96 hours will be analyzed in the Day 4 database.

- ANCOVA will be performed to compare the mean change between BIIB093 combined and placebo groups based on the observed data.
- By-visit mean and change in absolute edema volume from baseline will be summarized.

[figure not shown]
## Time to All-cause Death, Including Neurological Death, through Day 90

Survival time in days through Day 90 is defined as the time from randomization to death, including all-cause death and neurological death. For a participant who discontinues and is not known to have died during the study, survival time will be censored at the time when the participant is last known to be alive of the study. Survival time will be analyzed in the Day 90 database for all randomized participants.

- Survival time will be analyzed using Cox proportional hazards regression models of overall survival after adjusting for covariates specified in Section [5.6.1](#).
- Kaplan Meier curves of survival will be presented for BIIB093 3mg/day, BIIB093 5 mg/day, BIIB093 combined and placebo groups.

A horizontal bar chart consisting of 10 black bars of increasing length from left to right. The bars are set against a white background. The first bar is the shortest, and the 10th bar is the longest, extending almost to the right edge of the frame.

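### The hematoma-versus-edema objective compares hematoma at 24 hours with edema at 96 hours and plans no visible same-time comparison, so a drug acting equally on both may look selective

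*Protocol*

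**What the plan says.** Protocol section 6 (repeated in the synopsis) sets a secondary objective of distinguishing the drug's mechanism "by examining differential effects on hematoma and edema expansion". Three endpoints sit under it:

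- "Change in total contusion volume (hematoma plus perihematomal edema) as measured by brain imaging from baseline to 24 hours" (or before an earlier procedure)
- "Change in absolute hematoma volume from baseline to 24 hours"
- "Change in absolute edema volume from baseline to 96 hours"

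Total contusion change at 96 hours is the primary endpoint.

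SAP 5.6.3 gives each component its own model. For hematoma at 24 hours, "ANCOVA will be performed to compare the mean change between BIIB093 combined and placebo groups based on the observed data"; the edema section says the same for 96 hours. Beyond that the SAP plans descriptive output: "By-visit mean and change in absolute hematoma volume from baseline will be summarized" and "By-visit mean and change in absolute edema volume from baseline will be summarized". SAP 5.6.1 describes one covariate-adjusted model per endpoint, combined BIIB093 against placebo, with no contrast between endpoints. The interim list in SAP 4.1 repeats the pairing of hematoma at 24 hours with edema at 96 hours.

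On modality, the Hour 24 scan is NCCT. At Hour 96 the MRI read is used when both exist (SAP 3.4.1), while baseline is NCCT. Multiplicity is not controlled across primary and secondary endpoints (Protocol 16.2.2.1, SAP 5.6.1).

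**The concern.** The objective is comparative: does the drug act more on one component than on the other? The named component endpoints differ in three ways at once: the component, the time on a 96-hour infusion, and usually the imaging modality. A gap between the two results cannot be assigned to the component alone.

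Nor does any visible analysis estimate the gap. Two separate tests against placebo, one with p below 0.05 and one above, do not show that the two effects differ. With unadjusted p-values as the only formal output for the components, that is the reading a report could slip into.

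At stake is the mechanistic conclusion, not the primary analysis. Protocol 16.7 allows Phase 3 preparation to be accelerated after the interim analysis, whose imaging list carries the same mismatched pair, so an unsupported statement about selectivity could travel.

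**Working it through.** **The plan's own figure.** Protocol 16.8: difference 15 mL, SD 29 mL, 80 against 80, two-sided 5%. Noncentrality = 15 / (29 × √(2/80)) = 3.27. Power is 90.5% (normal) or 90.2% (t, 158 df), against about 90% stated. It reproduces, but it concerns total volume at 96 hours. The documents give no effect, SD or power for either component.

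**Set-up for a drug with no selectivity (all assumed).**

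- Effect at 96 hours: 15 / 2 = 7.5 mL on each component.
- Equal component SDs s that reproduce the total SD: s = 29 / √(2 + 2ρ). For ρ = 0, 0.3, 0.5, 0.7 this gives 20.5, 18.0, 16.7, 15.7 mL.
- ρ also serves as the correlation between the two effect estimates.
- f = share of the 96-hour hematoma effect already present at 24 hours, so the 24-hour effect is 7.5 × f.
- Significant means crossing the two-sided 5% limit in the direction of benefit; z = effect / (SD × √(2/80)).

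**Chance that only one component is significant**, ranges over ρ:

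| f | Hematoma effect at 24 h | Edema only, 24 h SD = s√f | Edema only, 24 h SD = s | Hematoma only, both SD cases |
|---|---|---|---|---|
| 0.25 | 1.9 mL | 50–53% | 59–74% | 0–8% |
| 0.50 | 3.8 mL | 30–40% | 50–53% | 0–14% |
| 0.75 | 5.6 mL | 15–31% | 26–38% | 2–19% |
| 1.00 | 7.5 mL | 7–23% | 7–23% | 7–23% |

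If the 24-hour SD shrinks in proportion to f, each one-sided pattern has 7–23% at every f. The same holds when both components are tested at 96 hours: power is 64–86% each, and neither pattern is favored.

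**The direction can reverse.** Take unequal assumed SDs (hematoma at 24 hours 10–15 mL, edema at 96 hours 18–25 mL) and ρ = 0.4. With f = 0.25, edema only occurs in 32–64% of trials. With f = 1, hematoma only occurs in 19–52%.

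**Which f applies is not settled.** Protocol 4.2 stresses progression in the first 12 hours; Protocol 4.5.1.3 allows hemorrhagic progression and edema up to 3 to 4 days.

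**What can be recovered.** With the same participants and covariates, ANCOVA effects add: total minus hematoma at 24 hours is the edema effect at 24 hours, and total minus edema at 96 hours is the hematoma effect at 96 hours. A numerical check gave the same coefficient both ways. A CI needs the covariance of the two estimates, which is not planned output. The subtraction is only approximate under the protocol's text, which imputes at 96 hours and puts modality in the primary model (16.2.2.2).

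**What a same-time contrast could detect.** SD of (edema minus hematoma) = s × √(2(1 − ρ)) = 29.0, 21.3, 16.7, 12.2 mL. The difference detectable with 80% power = (1.960 + 0.842) × SD × √(2/80) = 12.9, 9.4, 7.4, 5.4 mL.

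**The case against.** The objective is not served by two endpoints alone. Total volume at 24 hours is listed under it, and total volume at 96 hours is the primary endpoint, so matched-time point estimates follow by subtraction. SAP 3.4.4 takes edema from the same visit as total volume. The by-visit summaries, shown by treatment group, also allow unadjusted same-time differences for each component. This stands: the information is in the data and partly in the planned tables.

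Objectives, derived variables and ANCOVA endpoints are redacted in both documents, so same-time tests may exist there. This stands too; absence is shown only for visible text.

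The plan nowhere says that one significant and one non-significant p-value will be read as selectivity. And modality is common to both arms within each endpoint, so it does not by itself bias either randomized comparison. Both are fair; the difficulty lies in comparing across the two endpoints.

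A reader might infer that a non-selective drug is bound to look edema-selective, or that the trial cannot answer its mechanism question. The documents support neither. The first needs the mean effect to accrue over the infusion while the spread does not shrink with it, and the highest chance in the grid is 74%. The second overlooks the total-volume analyses and the by-visit summaries.

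Finally, a contrast in mL is no clean cure. With assumed placebo growth of 20 mL (edema) and 5 mL (hematoma), both cut by 40%, the effects are 8 and 2 mL and the contrast is 6 mL, although the proportional effect is equal. It is also low-powered. This limits the contrast to a supportive role.

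**Conclusion.** The mismatch is real and does not depend on any assumed number. An objective about differential effects rests on hematoma at 24 hours and edema at 96 hours, tested separately, with no visible adjusted estimate and CI for edema at 24 hours or hematoma at 96 hours, and no visible contrast. A drug acting equally on both components may therefore look selective.

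How often, and in which direction, depends on component trajectories and SDs that the documents do not give. With equal SDs, the chance of an edema-only result runs from 7% to 74% across the assumptions shown; with unequal SDs the pattern can turn toward hematoma. The primary analysis and the sample size are not affected. This is an inexpensive improvement to a secondary analysis.

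**What to change.** In SAP 5.6.3, keep the named endpoints and add the same covariate-adjusted ANCOVA, reporting the treatment difference with 95% CI, for both hematoma change and edema change at both Hour 24 and Hour 96.

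State that any conclusion about differential effect will rest on these same-time estimates and not on one p-value below 0.05 and one above. As support, report the edema-minus-hematoma difference in treatment effect at each time with its 95% CI, in mL, noting its scale dependence and low power.

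No scans are added: SAP Appendix 1 already provides central reads for all available time points. The cost is SAP wording, a few more models, and more secondary estimates without multiplicity adjustment, reported without new significance claims. If redacted analyses already cover this, a cross-reference from the objective is enough.
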